#### Registration Process

To register a patient, the following documents should be completed by the Research Nurse or Study Coordinator and emailed to [[contact]](mailto:[contact]) and the lead CROCC Study Coordinator:

- Registration Form
- Signed patient consent form
- Eligibility Screening Checklist
- Copies of source documents, as applicable.

Study treatment cannot begin until the patient is registered.

The Research Nurse or Study Coordinator at the participating site will then e-mail ([[contact]](mailto:[contact]) and the lead CROCC Study Coordinator) the Coordinating Center to verify eligibility. To complete the registration process, the Coordinating Center will:

- Assign a patient study number
- Register and randomize the patient on the study
- Email the patient study number to the participating site

### 6.3. Stratification

In this study, patients will be stratified by gender and receipt of SOC drugs/vaccine.

### 6.4. Baseline studies

1. COVID-19 symptoms
2. COVID-19 NP swab with RT-PCR testing

#### **Optional (pending resource availability):**

1. Comprehensive metabolic panel (Na, K, Cl, BUN, Cr, Ca, Tot Protein, Alb, bilirubin, AST, ALT, Alk phos, HCO3)
2. Complete blood count w/differential
3. Clinical severity markers: ESR, CRP, D-dimer, ferritin, CK
4. Serum ultrasensitive PSA, testosterone (free and total), estradiol, luteinizing hormone, follicle stimulating hormone
5. Research NP swab for quantitative viral load
6. Blood and sputum sample for quantitative viral load (if resources permit) (~20cc of blood)
7. Research blood draw for banking (to be grouped with clinical blood draws) (~10cc of blood)

### 6.5. Treatment period

Patients will be followed according to the study calendar (Section 10). Patients in all arms will have telemedicine or audio telephone call at day 3, 7, 21, and day 60 to assess toxicity and recovery. If patients are admitted to the hospital during follow up, we will get information from the medical records.

Patients will be instructed to monitor for emergency warning signs. This includes, but is not limited to: trouble breathing, persistent pain or pressure in the chest, new confusion, inability to wake or stay awake, bluish lips or face. If any of these occur, patients will be instructed to call 911 or go to her/his local emergency facility for further evaluation.

#### 6.6. End of initial treatment

After 7 days of oral therapy, treatment will stop and patients will be followed as per section 10 (study calendar).

#### 6.7. Assessing the primary outcome

Patients will be followed for admission to the hospital. Electronic medical records, including EPIC at JHH and CRISP (throughout Maryland and surrounding states) will be queried for hospital admission. If patients report a hospital admission outside of these systems, records will be collected from the corresponding hospital.

#### 6.8. End of study

Day 60

#### 6.9. Early discontinuation

The reason for study removal and the date the subject was removed will be documented in the CRF. A subject must be discontinued from the trial for any of the following reasons:

- The subject withdraws consent.

A subject must be discontinued from treatment (but may continue to be monitored in the post-treatment follow up portion of the trial for any of the following reasons:

- The subject or legal representative (such as legal guardian) withdraws consent.
- Intercurrent illness that prevents further administration of treatment,
- Patient is hospitalization due to COVID-19,
- Unacceptable toxicity, as listed in section 6.10,
- If in the opinion of the Investigator, a change or temporal or permanent discontinuation of therapy would be in the best interest of the patient,
- Noncompliance with trial treatment or procedure requirements,
- Patient is lost to follow-up,
- Patient becomes pregnant

Patients who discontinue treatment will remain on study unless one of the above reasons for discontinuation from the study are met. The patients who discontinue treatment will continue to be followed as specified in section 10 (study calendar), per study protocol.

#### 6.10. Definition of unacceptable toxicities

Unacceptable toxicities are defined as:

- Any treatment-related  $\geq$  grade 3 AEs possibly related to the agents
- Any AE, laboratory abnormality, or intercurrent illness which, in the judgment of the investigator, presents a substantial clinical risk to the subject with continued bicalutamide or camostat dosing.

## 6.11. Definition of an overdose

An overdose is defined as the accidental or intentional administration of any dose of a product that is considered both excessive and medically important.

All occurrences of overdose must be reported as SAEs (see section 7.1.2 and 7.5).

### ***Bicalutamide***

A single dose of bicalutamide that results in symptoms of an overdose considered to be life threatening has not been established.

In the management of an overdose with bicalutamide, vomiting may be induced if the patient is alert. Dialysis is not likely to be helpful since bicalutamide is highly protein bound and is extensively metabolized. General supportive care, including frequent monitoring of vital signs and close observation of the patient, is indicated.

### ***Camostat***

There is no known information on overdose of camostat.

## 6.12. Survival

Patient records will be monitored for 60 days for vital status. For patients who have died, date of death will be collected, and overall survival duration will be calculated from randomization to death.

# 7. Adverse Events

## 7.1. Definitions

Toxicities will be graded using the NCI's Common Terminology Criteria for Adverse Events (CTCAE) Version 5.0:

[https://ctep.cancer.gov/protocolDevelopment/electronic\\_applications/ctc.htm](https://ctep.cancer.gov/protocolDevelopment/electronic_applications/ctc.htm)

In those cases where the NCI criteria do not apply, intensity will be defined as:

- Mild: awareness of symptom or sign, but easily tolerated
- Moderate: discomfort is enough to cause interference with normal activities
- Severe: inability to perform normal daily activities
- Life threatening: immediate risk of death from the reaction as it occurred

### 7.1.1. Adverse Event

An AE is defined as any undesirable sign, symptom or medical condition occurring after starting the study drug (or therapy) even if the event is not considered to be related to the study. An undesirable medical condition can be symptoms (e.g., nausea, chest pain), signs (e.g., tachycardia, enlarged liver) or the abnormal results of an investigation (e.g., laboratory findings, electrocardiogram). Medical conditions/diseases present before starting the study treatment are only considered AEs if they worsen after starting the study treatment (any procedures specified in the protocol). New medical conditions / diseases occurring before starting the study treatment but after signing the informed consent form will not be recorded as AEs.

Laboratory abnormalities: Laboratory abnormalities present at the screening visit will be recorded as pre-treatment signs and symptoms. After study treatment administration, all grade 3 and 4 clinical laboratory results that represent an increase in severity from baseline

will be reported as AEs. A grade 1 or 2 clinical laboratory abnormality should be reported as an AE only if it is considered clinically significant by the investigator (induce clinical signs or symptoms or require corrective therapy), meets the definition of an SAE, or requires the participant to have study drug discontinued or interrupted. It is expected that wherever possible, the clinical rather than laboratory term would be used by the reporting investigator (e.g., anemia versus low hemoglobin value).

### 7.1.2. Serious Adverse Event

A SAE is an undesirable sign, symptom or medical condition which:

- Results in death
- Is life threatening (defined as an event in which the subject was at risk of death at the time of the event; it does not refer to an event which hypothetically might have caused death if it were more severe)
- Requires inpatient hospitalization or causes prolongation of existing hospitalization (see note below for exceptions)
- Results in persistent or significant disability/incapacity
- Is a congenital anomaly/birth defect (note: reports of congenital anomalies/birth defects must also be reported on the Pregnancy Form)
- Is an important medical event (defined as a medical event(s) that may not be immediately life-threatening or result in death or hospitalization but, based upon appropriate medical and scientific judgment, may jeopardize the subject or may require intervention [e.g., medical, surgical] to prevent one of the other serious outcomes listed in the definition above.) Examples of such events include, but are not limited to, intensive treatment in an emergency room or at home for allergic bronchospasm; blood dyscrasias or convulsions that do not result in hospitalization.)
- Suspected transmission of an infectious agent (e.g., pathogenic or nonpathogenic) via the study drug is an SAE.
- Is a new cancer
- Is associated with an overdose (as defined in section 5.11)
- Is a pregnancy or pregnancy outcome of spontaneous abortion, missed abortion, benign hydatidiform mole, blighted ovum, fetal death, intrauterine death, miscarriage, or stillbirth.

Events not considered to be SAEs are hospitalizations for:

- Admission for progression of COVID-19-related symptoms
- A visit to the emergency room or other hospital department <24 hours, that does not result in admission (unless considered an important medical or life-threatening event)
- Admissions as per protocol for a planned medical/surgical procedure or to facilitate a procedure
- Routine health assessment requiring admission for baseline/trending of health status (e.g., routine colonoscopy)
- Medical/surgical admission for purpose other than remedying ill health state and was planned prior to entry into the study. Appropriate documentation is required in these cases.
- Admission encountered for another life circumstance that carries no bearing on health status and requires no medical/surgical intervention (e.g., lack of housing, economic inadequacy, care-giver respite, family circumstances, administrative).

### 7.2. Relationship

The relationship of an AE to the administration of the study drug is to be assessed by the investigator according to the following definitions:

- No (unrelated, not related, no relation): The time course between the administration of study drug and the occurrence or worsening of the adverse event rules out a causal relationship and another cause (concomitant drugs, therapies, complications, etc.) is suspected.
- Yes (related): The time course between the administration of study drug and the occurrence or worsening of the adverse event is consistent with a causal relationship and no other cause (concomitant drugs, therapies, complications, etc.) can be identified.

The following factors should also be considered:

- The temporal sequence from study drug administration - The event should occur after the study drug is given. The length of time from study drug exposure to event should be evaluated in the clinical context of the event.
- Underlying, concomitant, intercurrent diseases - Each report should be evaluated in the context of the natural history and course of the disease being treated and any other disease the subject may have.
- Concomitant medication - The other medications the subject is taking or the treatment the subject receives should be examined to determine whether any of them might be recognized to cause the event in question.
- Known response pattern for this class of study drug - Clinical and/or preclinical data may indicate whether a particular response is likely to be a class effect.
- Exposure to physical and/or mental stresses - The exposure to stress might induce adverse changes in the recipient and provide a logical and better explanation for the event.
- The pharmacology and pharmacokinetics of the study drug - The known pharmacologic properties (absorption, distribution, metabolism, and excretion) of the study drug should be considered.

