## 7.5. Reporting

Information about all adverse events, whether volunteered by the subject, discovered by investigator questioning, or detected through physical examination, laboratory test or other means, will be collected, recorded, and followed as appropriate.

All adverse events experienced by subjects will be collected and reported from the first dose of study drug, throughout the study, and will only be followed for 28 days unless related to the investigational agent.

Subjects who have an ongoing adverse event related to the study procedures and/or medication(s) may continue to be periodically contacted by a member of the study staff until the event is resolved or determined to be irreversible by the investigator.

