### 7.5.1. SAE Reporting

All SAEs (including deaths) occurring from the first dose of the study drug through 28 days after the last dose of study drug will be collected and recorded on the Adverse Event Case Report Form (CRF).

All SAEs should be reported to the IND Sponsor ([contact]) and Ono Pharmaceutical Co., Ltd ([contact]) within 24 hours of becoming aware of the event occurrence using the **SAE Reporting Form**. **Section 12.3** outlines reporting requirements for the DSMB.

SAEs will be reported to the Johns Hopkins Medicine IRB per institutional guidelines.

Adverse events that are serious, unexpected, and assessed by the investigator to be related to the study drug will be reported within 24 hours of becoming aware of the event occurrence to the post-marketing departments of the drug manufacturer.

After the initial SAE report, the investigator is required to proactively follow each subject and provide further information in regards to the subject's condition.

All AE(s) and SAE(s) will be followed until:

- Resolution
- The condition stabilizes
- The event is otherwise explained
- The subject is lost to follow-up
- Death

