### 7 Calendar-Day Telephone or Fax Report:

The IND Sponsor is required to notify the FDA of any fatal or life-threatening adverse event that is unexpected and assessed by the investigator to be possibly related to the investigational agent. Such reports are to be submitted to the FDA within 7 calendar days of

first learning of the event. Follow-up information will be submitted to the FDA as soon as relevant information is available.

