**15 Calendar-Day Written Report:**

The IND Sponsor is required to notify the FDA of any SAE that is unexpected and related to the investigational agent in a written IND Safety Report.

Written IND Safety Reports should include an Analysis of Similar Events in accordance with regulation 21 CFR § 312.32. All safety reports previously filed with the IND concerning similar events should be analyzed. The new report should contain comments on the significance of the new event in light of the previous, similar reports.

Written IND safety reports with Analysis of Similar Events are to be submitted to the FDA within 15 calendar days of first learning of the event. Follow-up information will be submitted to the FDA as soon as relevant information is available.

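### The Yes/No relatedness scale in 7.2 has no place for an event with compatible timing and another possible cause, and it does not match the terms in 6.10 and the FDA 7-day report

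*Combined protocol and SAP*

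**What the plan says.** Section 7.2 offers two grades, each made of two conditions joined by *and*. *No* applies when the time course "rules out a causal relationship and another cause (concomitant drugs, therapies, complications, etc.) is suspected". *Yes* applies when the time course "is consistent with a causal relationship and no other cause (concomitant drugs, therapies, complications, etc.) can be identified". A list introduced by "The following factors should also be considered" follows. It covers timing, underlying disease, concomitant medication, class effects, stress and pharmacology, but does not say where an event meeting neither definition goes.

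Other sections draw on this assessment in differing terms:

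- **2.5 and 11.2:** the proportion with drug-related AEs and SAEs is a secondary endpoint, compared by chi-squared test.
- **6.10, first bullet:** calls the events treatment-related and, in the same line, "grade 3 AEs possibly related to the agents". Under 6.9, unacceptable toxicity ends treatment.
- **FDA 7-day report:** fatal or life-threatening events that are "unexpected and assessed by the investigator to be possibly related to the investigational agent".
- **FDA 15-day report:** "any SAE that is unexpected and related to the investigational agent".
- **7.4 (reports to investigators) and 7.5.1 (manufacturer's post-marketing department):** *related*.
- **7.5:** adverse events "will only be followed for 28 days unless related to the investigational agent". Section 7.5.1, by contrast, states: "All AE(s) and SAE(s) will be followed until", and lists resolution, stabilisation, another explanation, loss to follow-up or death.

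**The concern.** A two-grade scale works only if every event falls into exactly one grade. Here an identifiable alternative cause bars *Yes* and compatible timing bars *No*, so an event with both features has no grade. This is not a rare case. Inclusion criterion 4 requires a COVID-19 symptom, and 7.2 itself tells the assessor to weigh the disease being treated. Nausea, vomiting and diarrhoea are entry symptoms in 3.1 and listed reactions to both drugs in 8.1 and 8.2. Cough and shortness of breath are entry symptoms and listed for bicalutamide. AST and ALT are disease-course markers in 2.6 and listed drug effects.

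At stake are a secondary safety endpoint, the relatedness-triggered reports and the length of follow-up. Section 11 says the safety findings will inform a larger trial. Assessment is open-label (4.1) and the protocol provides for several sites (13), so nothing in the design forces assessors to fill the gap in the same way.

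**Working it through.** The plan states no figure on this point, so there is none to reproduce. The check is one of logic, followed by two illustrations of size.

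**1. The two definitions against all combinations.**

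| Time course | Other cause | Grade under 7.2 |
|---|---|---|
| Consistent | None identified | Yes |
| Ruled out | Suspected | No |
| Consistent | Suspected or identified | Neither |
| Ruled out | None identified | Neither |

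Two of four cells are empty. The last matters little: any assessor would call an event with excluded timing unrelated. The third is the defect.

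**2. Terms used downstream.** *Related* appears in 7.4, the manufacturer report in 7.5.1, the 15-day report and the 28-day exception in 7.5. *Possibly related* appears in 6.10 and the 7-day report and is defined nowhere. So there is one defined term and one undefined term. A fatal unexpected event and a non-fatal serious one are tested against different words, although the assessor has recorded only Yes or No.

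**3. How much overlap the documents show.** Matching adverse-reaction terms to the Appendix A symptom list (approximate, e.g. asthenia with fatigue, pharyngitis with sore throat):

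- Bicalutamide, Table 1 of 8.2: 13 of 52 terms. By counts in the CASODEX column, 524/2167 = 24%. The source is a prostate cancer population on an added LHRH analog, so it is a weak guide.
- Camostat, other adverse reactions in 8.1: about 6 to 7 of 13 non-laboratory terms.

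The overlap is substantial, but this is not evidence of a majority of events.

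**4. Effect on the endpoint.** Inputs: 20 per arm (section 11) and the chi-squared test (11.2). Assumption: no control patient can have a drug-related event, since none receives study drug. If *k* treated patients have only ungraded events, the treated-arm proportion can be reported as anything from 0/20 to *k*/20. For *k*/20 against 0/20, uncorrected chi-squared = 40 × (20*k*)² / (20 × 20 × *k* × (40 − *k*)):

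- *k* = 3: 40 × 3600 / (400 × 3 × 37) = 144000/44400 = 3.24, p = 0.072
- *k* = 4: 40 × 6400 / (400 × 4 × 36) = 256000/57600 = 4.44, p = 0.035

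| k | Chi-squared, uncorrected | Yates | Fisher, two-sided |
|---|---|---|---|
| 3 | 0.072 | 0.230 | 0.231 |
| 4 | 0.035 | 0.114 | 0.106 |
| 5 | 0.017 | 0.056 | 0.047 |

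Section 11.2 does not say whether a continuity correction applies. Under the uncorrected test, grading one further patient (the fourth) crosses 0.05; under Fisher it is the fifth.

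**The case against.** The strongest reply is that most safety duties do not use relatedness at all. Section 7.1.1 counts an event as an AE whatever its cause, and 7.5 collects all AEs. Section 7.5.1 sends all SAEs to the IND sponsor and the camostat manufacturer within 24 hours, and 12.3 sends every SAE and death to the DSMB. The second bullet of 6.10 rests on the investigator's judgement of risk. All of this stands. A reader might infer that safety reporting as a whole cannot be applied; the documents do not support that. (Section 7.1.2 excludes admissions for worsening COVID-19 from the SAE definition, but that is a separate rule and not a product of the 7.2 scale.)

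Three other stronger readings also fail:

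- **That most on-treatment events are ungraded.** No event distribution is given, and under 7.1.1 conditions present before treatment count only if they worsen, so unchanged baseline symptoms never reach 7.2.
- **That toxicity will be under-counted.** A strict reader can rarely tick *Yes*, but can rarely tick *No* either, since *No* needs timing that excludes the drug. Investigators could default either way.
- **That three thresholds are in use.** The absence of another cause is part of 7.2's definition of *related*; it is not a further threshold.

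It can also be said that the listed factors guide judgement, and that the Protocol Chair reviews SAEs and data from all sites in a 40-patient study. Both may reduce inconsistency. Neither supplies a default grade or defines *possibly related*.

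**Conclusion.** The point holds in limited form and should be fixed. The 7.2 scale is not exhaustive, and the empty cell that matters holds any event with compatible timing and another possible cause. *Possibly related* in 6.10 and the 7-day report has no counterpart in 7.2. What cannot be applied consistently is the drug-related AE/SAE endpoint, the expedited, FDA and manufacturer reports, the follow-up exception beyond 28 days, and the first bullet of 6.10. The primary endpoint is untouched.

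The logical gap needs no assumption beyond reading the definitions as written. The numerical illustration rests on 20 per arm and no drug-related events in control; it shows that grading a single patient can move the endpoint comparison across 0.05. It does not show how often ungraded events will occur or which way they will be resolved.

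**What to change.** - Replace the definitions in 7.2 with an exhaustive, mutually exclusive pair. *Related*: there is a reasonable possibility that the study drug caused the event, even if another cause such as COVID-19 is also possible. *Not related*: there is no reasonable possibility.
- State in 2.5 that *related* in this sense is what counts as drug-related for the endpoint.
- Use that one term in 7.4, 7.5.1, both FDA reports and the CRF.
- Reconcile 6.10 with 7.2. Because 6.10 governs stopping of treatment, its threshold is for the investigators to settle; none is proposed here.
- Reconcile the AE follow-up rules in 7.5 and 7.5.1.

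The cost is protocol wording and one CRF field. The downside is that somewhat more events will be classed as related and reported.

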### 7.3. Expectedness

Unexpected AE: An AE, which varies in nature, intensity or frequency from information on the investigational drug/agent provided in the product IB, package insert or safety reports. Any AE that is not included in the IB, package insert, safety reports or informed consent is considered “unexpected”. An expected AE with a fatal outcome should be considered unexpected unless the IB specifically states that the AE might be associated with a fatal outcome.

Expected (known) AE: An AE, which has been reported in the IB, package insert or safety reports. An AE is considered “expected”, only if it is included in the IB document as a risk.

